Statistical and Database Management Resource: The ICTR is highly regarded for database development incorporating multiple layers of protection. The Director of the ICTR, [name], trained and supervised the Ketamine Team in developing the REDCap database to enter, save, protect and prepare to export for analysis, the data generated in this project. The benefits of the REDCap database include: firewall behind the existing JHU firewall, establishing restricted and unrestricted accessibility modes to ensure IRB protected data remain accessible only to individuals listed on the IRB, compartmentalizing tasks, and running the latest antiviral and anti-hacking software. Data integrity is assured using multiple methods, including utilizing variable definitions and data dictionary (item name and definition, scale, range, out of range and multiple key hit detectors). The complexity of this database is necessitated by the elegant and rigorous study design with 14 repeated measures over 7 consecutive days, which will entail multilevel analysis of time varying and time invariant data. Each variable is coded by day (1-7) and session (1-14), as well as data input quality such as double entry, blinded data collection and data entry, automated checks, auto scoring programs, time lapse between recording and entry, standardized data collection forms, and, enhanced study-specific Manual of Operations for the Safety, Efficacy and Opiate-Sparing Effects of Ketamine for Acute Burn Wound Care Pain in a Setting Analogous to Austere Battlefield Conditions (IRB00089761). The Manual was adapted from a previously developed Manual that was successfully utilized by [name] and his team for Management, Operations, and Evaluating Progress towards Goals. It contains a wealth of detailed information that identify topics covered, specificity of instructions for involved personnel, roles, tasks, timelines, procedures and to ensure adequacy of documentation.

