# 7. Study Statistics

- a. Primary outcome variable. Described above (Outcomes)
- b. Secondary outcome variables. Described above (Outcomes)
- c. Statistical plan including sample size justification and interim data analysis. Described above

Statistical consultation and initial power estimation were obtained from the Johns Hopkins Biostatistics, Epidemiology, and Database program (BEAD). The Johns Hopkins Institute for Clinical and Translational Research (ICTR) worked with the Ketamine Team to develop the randomization model and the REDCap Database and will continue to serve as consultants throughout the duration of the study. The ICTR expertise will be of particular importance when managing issues such as data cleaning and preparation, preparing interim reports, and in designing and conducting both preliminary and final statistical analyses. Using standard methods, the BEAD suggested that a total sample size of 74-94 participants (n= 37-47 per Condition) should be sufficient to provide a power of .85 to detect a statistically significant difference at p < 0.05. This study team has discussed this issue of power and decided to be conservative and enhance the opportunity of making a definitive statement regarding study objectives and secondary questions. Therefore, the total target sample size will be increased to n= 100. One clarification is important: Funding is for a 1-year period. Should funding end before 94 participants are enrolled the study will have more than sufficient power to address the primary objectives (n=74).

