# Data Analysis Plan

[name], a professional biostatistician from the JH BEAD program specializing in clinical trials and longitudinal data analysis, had assisted Drs. [name] and [name] in conducting the statistical analyses in consultation with Going forward, this role will be assumed by biostatisticians at the JHU-ICTR.

The primary data analyses (Pain variables) will be conducted using analysis of covariance, or, longitudinal growth modeling (if normality assumptions are met) to examine group differences both in cross-section and longitudinally. If normality assumptions are violated then appropriate nonparametric tests will be utilized (e.g., Wald statistic). These methods allow for statistical controlling multiple potential confounding baseline variables and are robust against dropout - expected to be minimal. Data from the following study were used to generate this power estimate (Beaudoin, 2014).

Prior to study start-up, it is anticipated that, since ANCOVA is the recommended procedure for analyzing pre- to post- treatment change scores, that is the test that will be utilized for the primary aim, because: it is more powerful than t-test and Mann-Whitney; it can adjust for baseline group differences; it can be adjusted for baseline randomization strata; and, it can be utilized in analyzing repeated measures such as in the present study.

Prior to testing hypotheses, univariate distributions of variables will be inspected to assess normality, identify outliers, skewness or other abnormalities in distribution, determine appropriate summaries of location and spread and the need for transformation or nonparametric analysis. Preliminary analyses will determine whether the data meet basic assumptions for parametric tests. If relevant covariates are not balanced by the randomization, or confounds are distributed unevenly across groups, they will be included in the models as covariates.

If Pain Intensity is substantially associated with non-study factors (e.g., age, gender, TBSA) these variables will be statistically controlled as indicated in analyses.

The data on average (or summed) Opiate Sparing Effects from baseline to post-treatment, and within group and between group changes over time are likely not to meet criteria for parametric analysis, that is, they are expected to be non-normally distributed and thus inappropriate for Analysis of Covariance (ANCOVA).

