It is anticipated that the data on Opiate Sparing (i.e., requested additional dose of analgesic medication) will be non-normal and will be analyzed using Mann-Whitney or other nonparametric method as appropriate. Prior to testing hypotheses, univariate distributions of variables will be inspected to assess normality, identify outliers, skewness or other abnormalities in distribution, determine appropriate summaries of location and spread and the need for transformation or nonparametric analysis. Preliminary analyses will determine whether the data meet basic assumptions for parametric tests. If relevant covariates are not balanced by the randomization, or confounds are distributed unevenly across groups, they will be included in the models as covariates. If Opiate Sparing is substantially associated with non-study factors (e.g., age, gender, TBSA) these variables will be statistically controlled as indicated in analyses.

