# Trajectory, and, Mediator / Moderator Analyses

Finally, analyses will be conducted that take into account the variability of participant's responses over time. It is anticipated that these analyses may yield significant insight into patterns of Time and Time-by-Group responses that are not easily disentangled using traditional statistical methods. Thus, statistical analyses will include methods (e.g., latent growth mixture modeling, latent class growth curve analysis) to identify classes of patients with similar trajectories and mediator/moderator variables that effect outcome (e.g., stability, resilience, impairment). It is anticipated that these methods will enable identification of participants at greater or lesser risk for chronic pain and ongoing psychological distress. The potential impact on the quality of care, soldier safety and comfort, and early identification and risk stratification – possibly under austere battlefield conditions during the first painful procedures – cannot be over-estimated.

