# **Participant Dropout**

Dropouts and participants whose wound care ends or changes substantially prior to the anticipated 7day study period will be handled on an intent-to-treat manner in all key analyses with the last data obtained treated as the endpoint for that participant. Reasons for dropout will be recorded and contrasted across group.

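### Aim 2 is a primary objective, but the plan fixes neither the summary of requests over 3 to 14 sessions, nor the covariate-adjusting method, nor what the last-data rule means for a count

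*Combined protocol and SAP*

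**What the plan says.** Section 2 (Objectives) lists Specific Aims 1 and 2 as primary. Aim 2 is measured by the number of requests for extra analgesic at each of the 14 procedures. No patient-level summary is given there.

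In section 7, the Data Analysis Plan refers to "average (or summed) Opiate Sparing Effects from baseline to post-treatment". It does not choose between average and sum, and I find no baseline request count defined. It calls ANCOVA unsuitable for this outcome and expects that the data "will be non-normal and will be analyzed using Mann-Whitney or other nonparametric method as appropriate".

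On covariates, unbalanced ones are to enter the models, and "If Opiate Sparing is substantially associated with non-study factors (e.g., age, gender, TBSA) these variables will be statistically controlled as indicated in analyses". No threshold and no adjusting method are given. Distributions are to be inspected before hypotheses are tested, to settle the summaries and the type of analysis. The plan does not say that this is done blind to arm.

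Under Participant Dropout, patients who drop out, or whose wound care ends or changes early, are "handled on an intent-to-treat manner in all key analyses with the last data obtained treated as the endpoint for that participant". The Changes Requested section allows 3 to 14 sessions, and the corrected sample size assumes 11 on average.

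Two other places foresee longitudinal work: "14 repeated measures over 7 consecutive days, which will entail multilevel analysis of time varying and time invariant data" (database paragraph under Changes Requested) and "analyses will be conducted that take into account the variability of participant's responses over time" (Trajectory section). Neither names Aim 2. On power, section 7 says: "Should funding end before 94 participants are enrolled the study will have more than sufficient power to address the primary objectives (n=74").

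**The concern.** A test has been named for a primary outcome, but the variable it is to be applied to has not. When patients have between 3 and 14 sessions, a raw sum measures length of stay as well as demand for analgesia, while an average does not. The last-data rule was evidently written with a score in mind. For a count it can mean the last session alone, or the last count repeated up to session 14. Early end of wound care is an expected course here, so the rule would reach many patients.

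The covariate promise has a similar gap: plain Mann-Whitney takes no covariates, parametric ANCOVA is set aside, and covariates are to be picked by what is observed. What is at stake is mainly power for a primary objective, together with a choice of summary and covariates that stays open until the data are seen.

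**Working it through.** **The plan's own figure.** The only sample-size derivations concern mean NAS pain. Patients per arm = n × [1 + (m − 1) × ICC] / m, where n comes from a two-sided two-sample t-test at 0.05 with 80% power for a difference of 2.0.

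- SD 4.0, m = 11, ICC 0.7: n = 64; 64 × 8.0 / 11 = 46.5, so 47. This matches the plan.
- SD 3.0, m = 14, ICC 0.7: n = 37; 37 × 10.1 / 14 = 26.7, so 27. This also matches.

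Neither uses a request rate, so there is no Aim 2 figure to reproduce.

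**Illustration.** From the documents: 47 per arm, 3 to 14 sessions, mean 11. Assumed: Poisson requests, 1 per session in control, rate ratio 0.7, gamma variation between patients with shape 1.5, 3 or 6 (high, medium, low), and the same distribution of stays in both arms. Sessions were either beta-binomial on 3 to 14 (mean 11.0, SD 2.6, 19% with all 14) or uniform on 3 to 14 (mean 8.5). The test was two-sided Mann-Whitney at 0.05, with 10,000 trials per cell (simulation error up to 0.5 points). In the last-session reading, early stoppers contribute their last session's count and patients with all 14 sessions contribute their average.

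Power in %, high / medium / low variation:

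| Reading | Mean 11 sessions | Uniform 3 to 14 |
|---|---|---|
| Requests per attended session | 40.7 / 66.6 / 86.5 | 39.6 / 61.3 / 79.9 |
| Raw sum | 38.0 / 60.2 / 78.9 | 33.1 / 47.7 / 60.6 |
| Last count carried forward to session 14 | 37.8 / 60.3 / 79.2 | 33.6 / 49.7 / 63.3 |
| Last session for early stoppers | 20.9 / 28.4 / 34.1 | 20.7 / 26.0 / 29.5 |

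Sum against average: 2.7 / 6.4 / 7.6 points lost at mean 11, and 6.5 / 13.6 / 19.3 with uniform sessions.

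**Why the sum loses.** With mean rate 1 and K sessions, the squared coefficient of variation is

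- sum: 1/E(K) + CV²(K) + CV²(patient) + CV²(K) × CV²(patient);
- average: E(1/K) + CV²(patient).

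For uniform K on 3 to 14, E(K) = 8.5, the variance is (12² − 1)/12 = 11.92, CV²(K) = 11.92/72.25 = 0.165, and E(1/K) = 1.752/12 = 0.146. With shape 6, CV²(patient) = 1/6 = 0.167. The sum gives 0.118 + 0.165 + 0.167 + 0.027 = 0.477; the average gives 0.146 + 0.167 = 0.313. The excess is noise from length of stay.

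**Sensitivity.**

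- Control rate 0.5 to 2 per session: the sum loses 2 to 8 points (mean 11) or 4 to 22 (uniform).
- 37 per arm, mean 11: sum 31 / 50 / 68%, average 33 / 56 / 77%.
- Requests falling 15% per session, mean 11: sum 36.4 / 56.1 / 72.3%, average 35.8 / 55.4 / 71.2%. The sum's loss disappears. The last-session reading drops to 9 to 11%.
- No effect, equal stays: each of the four readings rejects in 4.5 to 5.1% of trials.

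**The case against.** The best defence is that the plan is under-specified, not silent. It names a default test and an intent-to-treat principle, records requests by session, and looks at distributions before testing. A method such as rank ANCOVA would fit within the nonparametric methods it allows. The Opiate Sparing sentence also mentions changes over time. All of that stands, but none of it says what variable enters the test, which covariates are used, or what happens to a patient who leaves after session 5.

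It can also be said that the widest contrast depends on the last-session reading, a mixed variable that no section describes. That is fair. Without it, the spread at the planned 11 sessions is 3 to 8 points. But the last-data rule covers all key analyses, so the reading is open until it is closed.

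Three stronger conclusions are tempting and not supported.

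- A reader might infer inflated type I error. The raw sum is inflated only if stays differ by arm, which no section states. Nor does any section allow picking the most favourable p-value.
- A reader might infer that Aim 2 is underpowered and the statement about n=74 wrong. The documents give no request rate or target effect, so this cannot be shown; the statement simply has no derivation for Aim 2.
- A reader might infer that a session-level count regression should replace the rank test. With gamma variation it gains 3 to 8 points over Mann-Whitney on the average; with lognormal variation the difference is −3 to +3. If 5% of patients request 4 or 5 times as often (assumed), its power falls to about 50% and 44%, against about 60% and 59% for the rank test, with null rejection of about 7%. Since the plan itself anticipates skewness and outliers, replacing the rank test is not justified.

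**Conclusion.** The point holds as a gap in specification for a primary objective, and it should be closed. Three things are open: the summary of requests, the adjusting method with its covariates, and the meaning of the last-data rule for a count. The consequence is loss of power: small to moderate for the sum or carry-forward, none for the sum if requests fall steeply, and severe for a last-session reading. There is also an open choice not stated to be blind to arm.

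The direction follows from the variable number of sessions. The sizes rest on assumed request rates, patient variation, effect and equal stays, and on a sample size derived for pain. They show that the readings differ, and do not predict power in this trial.

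**What to change.** 1. Remove the option to sum, and define the Aim 2 outcome as each patient's requests per attended session.
2. Keep the nonparametric approach but name one covariate-adjusting rank method, for example rank ANCOVA. Fix NAS before the first dose and TBSA as covariates in advance, instead of selecting by observed imbalance or association. Report unadjusted Mann-Whitney as a check. In simulations with lognormal variation, a baseline covariate explaining 10% or 30% of between-patient variance added 1 to 3 or 5 to 9 points of power.
3. State that the last-data rule does not apply to Aim 2, so that all attended sessions are used. Tabulate sessions by arm.
4. State that any remaining choice is made blind to arm.
5. Optionally add, as a sensitivity analysis only, a session-level count regression clustered by patient with session number, giving a rate ratio with 95% CI.

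The cost is SAP wording and programming; the data are already coded by day and session. Two downsides should be disclosed. Patients with few sessions contribute a noisier average. The average can also be distorted if requests trend over sessions and stays differ by arm: with no effect, requests falling 15% per session and ketamine stays 2 sessions shorter (all assumed), it rejected in 7 to 12% of trials. The table of sessions and the optional regression would reveal this.

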# Trajectory, and, Mediator / Moderator Analyses

Finally, analyses will be conducted that take into account the variability of participant's responses over time. It is anticipated that these analyses may yield significant insight into patterns of Time and Time-by-Group responses that are not easily disentangled using traditional statistical methods. Thus, statistical analyses will include methods (e.g., latent growth mixture modeling, latent class growth curve analysis) to identify classes of patients with similar trajectories and mediator/moderator variables that effect outcome (e.g., stability, resilience, impairment). It is anticipated that these methods will enable identification of participants at greater or lesser risk for chronic pain and ongoing psychological distress. The potential impact on the quality of care, soldier safety and comfort, and early identification and risk stratification – possibly under austere battlefield conditions during the first painful procedures – cannot be over-estimated.

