#### 1. Sample Size Estimate Based on Stay $\geq$ 7 days in Burn ICU.

The sample size calculation is based on the primary statistical procedure for this project which will test the difference in mean pain scores, defined as the average self-report of mean pain score, based on the Numeric Analogue Scale (NAS), during each burn wound care procedures, between individuals randomized to usual care plus placebo (fentanyl plus saline) and those randomized to the intervention arm (usual care + ketamine). PASS Sample Size (Version 14) was used to perform all sample size calculations while considering individuals over the one-year study duration randomized to control and intervention arms in a 1:1 fashion.

In the first case, we further assume that each individual, will, on average, have a length of stay of 7 days thus resulting in 14 wound care procedures performed during hospital stay. We determined the minimum sample size for our trial based on 80% power at p = 0.05 to detect a clinically significant difference in mean pain score during the wound care procedure of 2.0 points between the control and intervention arms with a standard deviation of 3.0. In addition, to account for the clustered nature of procedures performed on individuals, we have used a sample size inflator (also termed "design effect") of 10.1 as described by the Cochrane manual@ conservatively using an interclass correlation of effects of 0.7 amongst repeated measures of pain scores within each individual and 14 observations per individual.

The required sample size needed to accept the alternative hypotheses that the mean pain care score in the intervention arm decreased by 2 points compared to the control arm at the 0.05 level would require 27 individuals per arm (54 total), our anticipated population of 74 eligible individuals is adequate to show a clinically significant improvement for both intervention arms.

@http://handbook.cochrane.org/chapter\_16/16\_3\_4\_approximate\_analyses\_of\_cluster\_randomized\_trials\_for\_a.htm

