#### 2. Corrected Sample Size Estimate for Length of Stay on the Burn ICU $\geq$ 7 days as **estimated on Admission** but, however, where the **Actual Length of Stay on Burn ICU is** $\geq$ **5.5 days** because of Factors that either not present or not evident or were difficult to quantify at time of admission and consent of the patient.

This sample size calculation is based on the primary statistical procedure for this project which will test the difference in mean pain scores, defined as the average self-report of mean pain score, based on the NAS, during each burn wound care procedures, between individuals randomized to usual care (fentanyl plus saline) and those randomized to the intervention arm (usual care + ketamine). PASS Sample Size (Version 14) was used to perform all sample size calculations eligible individuals over the one-year study duration randomized to control and intervention arms in a 1:1 fashion.

In this situation, where Length of Stay is less than the initially estimated >7 days, we further assume that each individual, will, on average, have a length of stay of 5.5 days on the Burn ICU thus resulting in 11 wound care procedures

performed during hospital stay on the Burn ICU. We determined the minimum sample size for our trial based on 80% power at p = 0.05 to detect a clinically significant difference in mean pain score during the wound care procedure of 2.0 between the control and intervention arms with a standard deviation of 4.0. In addition, to account for the clustered nature of procedures performed on individuals, we have used a sample size inflator (also termed "design effect") of 8.0 as described by the Cochrane manual@ conservatively using an interclass correlation of effects of 0.7 amongst repeated measures of pain scores within each individual and 11 observations per individual.

The required sample size needed to accept the alternative hypotheses that the mean pain care score in the intervention arm decreased by 2 points compared to the control arm at the 0.05 level would require 47 eligible individuals (94 total), our anticipated population of 128 eligible individuals is adequate to show a clinically significant improvement for both intervention arms.

@http://handbook.cochrane.org/chapter\_16/16\_3\_4 approximate analyses\_of\_cluster\_randomized\_trials\_for\_a.htm

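### Latent class growth analysis, one of two example methods for finding trajectory classes, reports several classes under the plan's own ICC of 0.7 even when patients form one continuous population

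*Combined protocol and SAP*

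**What the plan says.** The Trajectory, and, Mediator / Moderator Analyses section (7. Study Statistics) states that "statistical analyses will include methods (e.g., latent growth mixture modeling, latent class growth curve analysis) to identify classes of patients with similar trajectories". Of their use it says: "It is anticipated that these methods will enable identification of participants at greater or lesser risk for chronic pain and ongoing psychological distress". It does not say how the number of classes is chosen, whether patients may vary within a class, or which one-class model the classes must improve on.

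Both sample size sections assume strong within-patient correlation of pain scores. The 7-day case works by "conservatively using an interclass correlation of effects of 0.7 amongst repeated measures of pain scores within each individual and 14 observations per individual", with a "standard deviation of 3.0". The corrected 5.5-day case works by "conservatively using an interclass correlation of effects of 0.7 amongst repeated measures of pain scores within each individual and 11 observations per individual", with a "standard deviation of 4.0".

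Two other places bear on the point. The Data Analysis Plan already names longitudinal growth modeling for the pain outcomes. Item 1(a) of the secondary outcomes already plans mean pain and individual trajectory, within and across sessions, as predictors of PTSD at 1 month.

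**The concern.** A class analysis used for risk stratification must be able to answer that there are no classes. The relevant null is one population whose pain levels vary continuously.

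Latent class growth analysis fixes within-class variance at zero. Its one-class model therefore says that all patients share one curve and that a patient's repeated ratings are independent around it. An ICC of 0.7 says the opposite. Rejecting that one-class model shows only that patients differ, which the plan already assumes. Any classes found may be slices of a continuum, and nothing in the section would prevent their being reported as distinct risk groups.

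**Working it through.** **1. The plan's ICC is a working input.** The sample size is the two-sided t-test n per arm (80% power, alpha 0.05, difference 2.0), times the design effect 1 + (m - 1) x ICC, divided by m.

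- Corrected case, SD 4.0, m = 11: design effect 1 + 10 x 0.7 = 8.0; 64 x 8.0 / 11 = 46.5, so 47 per arm, as stated.
- 7-day case, SD 3.0, m = 14: design effect 1 + 13 x 0.7 = 10.1; 37 x 10.1 / 14 = 26.7, so 27 per arm, as stated.

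**2. What the one-class model leaves out.** With SD 4.0 and ICC 0.7, the between-patient variance is 0.7 x 16 = 11.2 and the residual variance is 4.8. A patient's 11-session mean then has variance 11.2 + 4.8/11 = 11.64. One-class latent class growth analysis attributes all variance to independent residuals, giving 16/11 = 1.45. The ratio is 8.0, the plan's own design effect. Extra classes are the only way the method can absorb that gap.

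**3. Latent class growth analysis on data with no classes.** Data came from one population with a normal random intercept, a small common linear trend and no treatment effect. BIC chose the number of classes, with 100 runs per setting (50 for the quadratic one).

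| Setting | Runs choosing 2 or more classes | Classes chosen |
|---|---|---|
| N 94, 11 sessions, SD 4, ICC 0.7 | 100% | 5-7 |
| N 74, 14 sessions, SD 3, ICC 0.7 | 100% | 5-7 |
| N 54, 14 sessions, SD 3, ICC 0.7 | 100% | 4-7 |
| N 94, 11 sessions, SD 3, ICC 0.7, rounded and clipped to 0-10 | 100% | 4-6 |
| N 94, 11 sessions, SD 4, ICC 0.7, quadratic curves | 100% | 4-7 |
| N 94, 3 sessions, SD 4, ICC 0.7 | 100% | 3-5 |
| N 94, 11 sessions, SD 4, ICC 0.3 | 100% | 2-5 |
| N 94, 11 sessions, SD 4, ICC 0.1 | 94% | 1-3 |
| N 94, 11 sessions, SD 4, ICC 0 | 0% | 1 |

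A separate grid at N 94 and 11 sessions (SD 2, 3 or 4; ICC 0.4 or 0.7; bounded or not; at most 5 classes) gave 100% in all 12 settings.

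In the first row of the table, the median BIC gain of two classes over one was about 514 (minimum 352). The penalty for one more class is 3 parameters x ln 94 = 3 x 4.54 = 13.6, so a different penalty of ordinary size would not change the answer. Mean entropy was 0.91, so the false classes would look well separated.

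**4. Growth mixture modeling with within-class random effects (N 94, 11 sessions, ICC 0.7 unless stated).** On normal data it chose two or more classes in 0-3% of runs, including N 54 with 14 sessions. On ratings rounded and bounded to 0-10 the false-class rate depended on how many ratings sat at the limits (SDs are before clipping):

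| SD, mean | Up to 5 classes, 100 runs | Up to 3 classes, 60 runs |
|---|---|---|
| 2, 5.5 | 2% | not run |
| 3, 5.5 | 14% | 8% |
| 3, 4 | 32% | 13% |
| 3, 7 | 69% | 47% |
| 4, 5.5 | 66% | 47% |

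A random-intercept-only version at SD 3 and mean 5 gave 1% in 100 runs.

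**5. A normal bootstrap null is not enough.** One possible safeguard fits a normal one-class model to the bounded ratings, simulates from it, clips the result, and requires both BIC and the bootstrap test to favor classes. On one-population data both were passed falsely in about 23% (SD 4, mean 5.5) and 25% (SD 3, mean 7) of 40 runs. A second check with 60 runs gave 37% and 30%, and 5% at SD 3 and mean 5.5. The fitted normal model understates the latent spread, so clipping it again does not recreate the pile-up.

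**The case against.** The strongest reply is about consequence. The methods are given as examples and growth mixture modeling is listed first, so the plan does not commit to latent class growth analysis. The step lies outside the two primary objectives and the seven secondary outcomes. Item 1(a) of the secondary outcomes already supplies a continuous trajectory analysis for PTSD. All of this stands and limits the point.

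A reader might infer that the moderator and mediator conclusions rest on artificial groups. The documents do not support that: the moderators listed under the secondary outcomes (for example pain anxiety, catastrophizing, emotion regulation and resilience) are mostly measured scales. Nor do they support reading every named method as bound to find classes, given the 0-3% for growth mixture modeling on normal data.

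It is also fair that the section asks for groups with similar courses and not for proof of discrete types. Slices of a continuum can still order patients by risk, though cutting a continuous level into groups loses information.

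Finally, the section names neither the outcome nor a selection rule, and the ICC of 0.7 is a planning value the plan calls conservative. The result survives a much lower ICC (94% at 0.1). The bounded figures are softer. A latent SD of 4 at mean 5.5 becomes an observed SD of about 3.25 with 27% of ratings at 0 or 10, so it is not the plan's SD of 4.0.

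**Conclusion.** The concern holds for one of the two example methods. With no true classes and the plan's ICC, latent class growth analysis chose several classes in every simulated run, so it cannot serve as evidence that classes exist. Growth mixture modeling with within-class random effects is sound on normal data and only conditionally so on bounded ratings: its false-class rate ran from 1% to 69% depending on model, mean and spread.

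The reach is limited to the trajectory-class and risk-stratification statements. The primary and secondary treatment comparisons are unaffected.

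The figures rest on assumptions the documents do not give: selection by BIC, session pain score as the outcome, a normal random intercept, a small common trend and complete data. The result for latent class growth analysis is insensitive to the variations tried, other than an ICC near zero. The bounded mixture and bootstrap percentages are approximate.

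**What to change.** In the Trajectory, and, Mediator / Moderator Analyses section:

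- State that latent class growth curve analysis will not be used as evidence that classes exist.
- Make the one-class growth model with patient random intercept and slope the reference, and allow within-class random effects in any mixture model.
- Describe classes as distinct only if the mixture beats that reference on BIC and on a parametric bootstrap likelihood-ratio test. The bootstrap's one-class null should be fitted with a model for bounded ratings (for example censored/tobit or ordinal), not a normal model clipped afterwards. This version was not simulated here, so its false-class rate should be checked before use.
- Otherwise rely on the continuous intercept and slope as predictors, in line with item 1(a), and describe any groups as descriptive slices of a continuum.

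The cost is a few sentences and some computing time, with no new data or patients. The downside is that the trial may report no discrete classes.
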